## **7.5 USE OF COMPUTERIZED SYSTEMS**

When clinical observations are entered directly into a study site's computerized medical record system (ie, in lieu of original hardcopy records), the electronic record can serve as the source document if the system has been validated in accordance with health authority requirements pertaining to computerized systems used in clinical research. An acceptable computerized data collection system allows preservation of the original entry of data. If original data are modified, the system should maintain a viewable audit trail that shows the original data as well as the reason for the change, name of the person making the change, and date of the change.

## **7.6 RETENTION OF RECORDS**

Records and documents pertaining to the conduct of this study and the distribution of IMP, including eCRFs, electronic or paper patient-reported outcome data (if applicable), Informed Consent Forms, laboratory test results, and medication inventory records, must be retained by the Principal Investigator for at least 15 years after completion or discontinuation of the study or for the length of time required by relevant national or local health authorities, whichever is longer. After that period of time, the documents may be destroyed, subject to local regulations.

No records may be disposed of without the written approval of the Sponsor. Written notification should be provided to the Sponsor prior to transferring any records to another party or moving them to another location.

## **8. ETHICAL CONSIDERATIONS**

### **8.1 COMPLIANCE WITH LAWS AND REGULATIONS**

This study will be conducted in full conformance with the ICH E6 guideline for Good Clinical Practice and the principles of the Declaration of Helsinki, or the laws and regulations of the country in which the research is conducted, whichever affords the greater protection to the individual. The study will comply with the requirements of the ICH E2A guideline (Clinical Safety Data Management: Definitions and Standards for Expedited Reporting). Studies conducted in the United States or under a US Investigational New Drug (IND) Application will comply with US Food and Drug Administration regulations and applicable local, state, and federal laws. Studies conducted in the European Union (EU) or European Economic Area will comply with the EU Clinical Trial Directive (2001/20/EC).

## **8.2 INFORMED CONSENT**

The Sponsor's sample Informed Consent Form (and ancillary sample Informed Consent Forms such as a Child's Informed Assent Form or Mobile Nursing Informed Consent Form, if applicable) will be provided to each site. If applicable, it will be provided in a certified translation of the local language. The Sponsor or its designee must review and approve any proposed deviations from the Sponsor's sample Informed Consent Forms or any alternate consent forms proposed by the site (collectively, the "Consent Forms") before IRB/EC submission. The final IRB/EC-approved Consent Forms must be provided to the Sponsor for health authority submission purposes according to local requirements.

If applicable, the Informed Consent Form will contain separate sections for any optional procedures. The Investigator or authorized designee will explain to each subject the objectives, methods, and potential risks associated with each optional procedure. Subjects will be told that they are free to refuse to participate and may withdraw their consent at any time for any reason. A separate, specific signature will be required to document a subject's agreement to participate in optional procedures. Subjects who decline to participate will not provide a separate signature.

The Consent Forms must be signed and dated by the subject or the subject's legally authorized representative before his or her participation in the study. The case history or clinical records for each subject shall document the informed consent process and that written informed consent was obtained prior to participation in the study.

The Consent Forms should be revised whenever there are changes to study procedures or when new information becomes available that may affect the willingness of the subject to participate. The final revised IRB/EC-approved Consent Forms must be provided to the Sponsor for health authority submission purposes.

Subjects must be re-consented to the most current version of the Consent Forms (or to a significant new information/findings addendum in accordance with applicable laws and IRB/EC policy) during their participation in the study. For any updated or revised Consent Forms, the case history or clinical records for each subject shall document the informed consent process and that written informed consent was obtained using the updated/revised Consent Forms for continued participation in the study.

A copy of each signed Consent Form must be provided to the subject or the subject's legally authorized representative. All signed and dated Consent Forms must remain in each subject's study file or in the site file and must be available for verification by study monitors at any time.

## **8.3 INSTITUTIONAL REVIEW BOARD OR ETHICS COMMITTEE**

This protocol, the Informed Consent Forms, any information to be given to the subject, and relevant supporting information must be submitted to the IRB/EC by the Principal

Investigator and reviewed and approved by the IRB/EC before the study is initiated. In addition, any subject recruitment materials must be approved by the IRB/EC.

The Principal Investigator is responsible for providing written summaries of the status of the study to the IRB/EC annually or more frequently in accordance with the requirements, policies, and procedures established by the IRB/EC. Investigators are also responsible for promptly informing the IRB/EC of any protocol amendments (see Section 9.6).

In addition to the requirements for reporting all AEs to the Sponsor, investigators must comply with requirements for reporting SAEs to the local health authority and IRB/EC. Investigators may receive written IND safety reports or other safety-related communications from the Sponsor. Investigators are responsible for ensuring that such reports are reviewed and processed in accordance with health authority requirements and the policies and procedures established by their IRB/EC and archived in the site's study file.

#### **8.4 CONFIDENTIALITY**

The Sponsor maintains confidentiality standards by coding each subject enrolled in the study through assignment of a unique subject identification number. This means that subject names are not included in data sets that are transmitted to any Sponsor location.

Subject medical information obtained by this study is confidential and may be disclosed to third parties only as permitted by the Informed Consent Form (or separate authorization for use and disclosure of personal health information) signed by the subject, unless permitted or required by law.

Medical information may be given to a subject's personal physician or other appropriate medical personnel responsible for the subject's welfare, for treatment purposes.

Given the complexity and exploratory nature of exploratory biomarker analyses, data derived from these analyses will generally not be provided to study investigators or subjects unless required by law. The aggregate results of any conducted research will be available in accordance with the effective Roche policy on study data publication (see Section 9.5).

Data generated by this study must be available for inspection upon request by representatives of national and local health authorities, Sponsor monitors, representatives, and collaborators, and the IRB/EC for each study site, as appropriate.

#### **8.5 FINANCIAL DISCLOSURE**

Investigators will provide the Sponsor with sufficient, accurate financial information in accordance with local regulations to allow the Sponsor to submit complete and accurate financial certification or disclosure statements to the appropriate health authorities. Investigators are responsible for providing information on financial interests during the

course of the study and for 1 year after completion of the study (see definition of end of study in Section 3.2).

## **9. STUDY DOCUMENTATION, MONITORING, AND ADMINISTRATION**

### **9.1 STUDY DOCUMENTATION**

The Investigator must maintain adequate and accurate records to enable the conduct of the study to be fully documented, including, but not limited to, the protocol, protocol amendments, Informed Consent Forms, and documentation of IRB/EC and governmental approval. In addition, at the end of the study, the Investigator will receive the subject data, including an audit trail containing a complete record of all changes to data.

### **9.2 PROTOCOL DEVIATIONS**

The Investigator should document and explain any protocol deviations. The Investigator should promptly report any deviations that might have an impact on subject safety and data integrity to the Sponsor and to the IRB/EC in accordance with established IRB/EC policies and procedures. The Sponsor will review all protocol deviations and assess whether any represent a serious breach of Good Clinical Practice guidelines and require reporting to health authorities. As per the Sponsor's standard operating procedures, prospective requests to deviate from the protocol, including requests to waive protocol eligibility criteria, are not allowed.

### **9.3 SITE INSPECTIONS**

Site visits will be conducted by the Sponsor or an authorized representative for inspection of study data, subjects' medical records, and eCRFs. The Investigator will permit national and local health authorities; Sponsor monitors, representatives, and collaborators; and the IRBs/ECs to inspect facilities and records relevant to this study.

### **9.4 ADMINISTRATIVE STRUCTURE**

The Sponsor of the trial is F. Hoffmann-La Roche Ltd. The Sponsor has contracted PRA, who will be delegated responsibility for various aspects of this clinical trial.

One site will participate to enroll 14 to 18 subjects.

Central facilities will be used for certain study assessments throughout the study (eg, specified laboratory tests and PK analyses), as specified in Section 4.5. Accredited local laboratories will be used for routine monitoring; local laboratory ranges will be collected.

### **9.5 PUBLICATION OF DATA AND PROTECTION OF TRADE SECRETS**

Regardless of the outcome of a trial, the Sponsor is dedicated to openly providing information on the trial to healthcare professionals and to the public, both at scientific

congresses and in peer-reviewed journals. The Sponsor will comply with all requirements for publication of study results. For more information, refer to the Roche Global Policy on Sharing of Clinical Trials Data at the following Web site:

[www.roche.com/roche\\_global\\_policy\\_on\\_sharing\\_of\\_clinical\\_study\\_information.pdf](http://www.roche.com/roche_global_policy_on_sharing_of_clinical_study_information.pdf)

The results of this study may be published or presented at scientific congresses. For all clinical trials in subjects involving an IMP for which a marketing authorization application has been filed or approved in any country, the Sponsor aims to submit a journal manuscript reporting primary clinical trial results within 6 months after the availability of the respective Clinical Study Report. In addition, for all clinical trials in subjects involving an IMP for which a marketing authorization application has been filed or approved in any country, the Sponsor aims to publish results from analyses of additional endpoints and exploratory data that are clinically meaningful and statistically sound.

In accordance with standard editorial and ethical practice, the Sponsor will generally support publication of multicenter trials only in their entirety and not as individual center data. In this case, a coordinating investigator will be designated by mutual agreement.

Authorship will be determined by mutual agreement and in line with International Committee of Medical Journal Editors authorship requirements. Any formal publication of the study in which contribution of Sponsor personnel exceeded that of conventional monitoring will be considered as a joint publication by the Investigator and the appropriate Sponsor personnel.

Any inventions and resulting patents, improvements, and/or know-how originating from the use of data from this study will become and remain the exclusive and unburdened property of the Sponsor, except where agreed otherwise.

## **9.6 PROTOCOL AMENDMENTS**

Any protocol amendments will be prepared by PRA. Protocol amendments will be submitted to the IRB/EC and to regulatory authorities in accordance with local regulatory requirements.

Approval must be obtained from the IRB/EC and regulatory authorities (as locally required) before implementation of any changes, except for changes necessary to eliminate an immediate hazard to subjects or changes that involve logistical or administrative aspects only (eg, change in Medical Monitor or contact information).

## Appendix 1 Schedule of Activities

Procedures	Screening	Period 1							Period 2											Follow-up					
		-1	1	2 to 8	9	10	11	washout (at least 7 days)	-1	1	2	3	4	5	6 to 11	12	13	14	15	16	17 to 19	20	21	14 to 21 days postdose	
Informed consent	X																								
Inclusion and exclusion criteria	X	X																							
Demographic data	X																								
Medical history	X	X																							
Urine drug screen and urine alcohol test	X	X							X																
Urinalysis	X	X											X										X	X	
Serology	X																								
Coagulation a	X																								
Pregnancy test b	X	X							X																X
Balovaptan administration c			X	X	X	X								X	X	X	X	X	X	X	X	X	X		
PK sampling for Balovaptan and metabolites M2 and M3 d			X	X	X	X	X							X		X	X	X	X	X	X	X	X		
Itraconazole administration e									X	X	X	X	X	X	X	X	X	X	X	X	X	X	X		
PK sampling for Itraconazole and hydroxyl-itraconazole f														X	X n						X	X			
Genotyping sample		X																							
Physical examination	X								X														X g	X	
Height, body weight and BMI h	X	X							X																

## Appendix 1 Schedule of Activities (cont.)

iSee [Appendix 2](#) for specific ECG time points by study day

jSee [Appendix 2](#) for specific vital signs time points by study day

kPrior to breakfast

lAt predose (breakfast will be provided 30 minutes before dosing and completed within approximately 15 minutes prior to balovaptan or itraconazole dosing), and at 5, 9, and 11.5 hours post dose

mPredose

nAssessments performed on Days 6, 8, and 10

oAssessments performed on Day 17

pTest performed about 3 hours after the morning dose of balovaptan. On Day 4 in Period 2, when only itraconazole is dosed, the timing of the orthostatic challenge test should correspond to 3 hours after the time of balovaptan dosing in Period 2.

## Appendix 2

### Schedule of Pharmacokinetic Sampling, Electrocardiogram, and Vital Signs Measurements

Procedure Study Day	Predose	Hours post dose											
		1	2	3	4	5	6	8	10	12	16	24	
Blood sampling balovaptan, M2, and M3													
Period 1													
Day 1, 3, 5, 8, 9	X a												
Day 10	X a	X	X	X	X	X	X	X	X	X	X	X b	X b
Period 2													
Day 6, 8, 10, 13, 14, 16, 18, 19	X a												
Day 15	X a	X	X	X	X	X	X	X	X	X	X	X c	X c
Day 20	X a	X	X	X	X	X	X	X	X	X	X	X d	X d
Blood sampling itraconazole and hydroxyl-itraconazole													
Period 2													
Day 5	X a		X		X				X				
Day 6, 8, 10, 14, 15, 16, 18, 19	X a												
Day 20	X a		X		X				X				X c
12-lead electrocardiograms													
Period 1													
Days 1 and 10	X												
Period 2													
Day 1	X e												
Day 5, 6, 8, 10, 13, 15, 17, 20	X				X								
Vital signs													
Period 1													
Day 1	X												
Day 11 f													
Period 2													

## Appendix 2 Schedule of Pharmacokinetic, Immunogenicity, and Biomarker Samples (cont.)

Procedure Study Day	Predose	Hours post dose										
		1	2	3	4	5	6	8	10	12	16	24
Day 1	X e											
Day 6	X	X	X		X			X		X		
Day 8, 10, 13, and 17	X				X							
Day 15	X	X	X		X			X		X		
Day 21 f												

a10 minutes predose (or time matched, when not dosed)

bDay 11

cDay 16

dDay 21

ePre-AM dose

fPrior to discharge

3.0 Introduction

This Statistical Analysis Plan (SAP) describes the statistical methods that will be used during the analysis and reporting of data collected under F. Hoffmann-La Roche Ltd Protocol WP40609.

This SAP should be read in conjunction with the study protocol and electronic case report form (eCRF). This version of the plan has been developed using protocol Version 1.0 dated 18-May-2018 [2] and the final eCRF(s) dated 05-Jul-2018.

An approved and signed SAP is a requirement for database lock.

This SAP only covers the results that will be processed by the PRA Early Development Services (EDS) Biostatistics Department.

PRA EDS will perform the pharmacokinetic (PK), and safety and tolerability evaluation.

This SAP supersedes the statistical considerations identified in the protocol; where considerations are substantially different, they will be so identified. Any post-hoc or unplanned analyses, or significant changes from the planned analysis in this SAP performed to provide results for inclusion in the clinical study report (CSR) but not included in this SAP, will be clearly identified in Section 9.8.2 of the CSR. Changes to planned analyses do not require an updated SAP but should be included in the CSR if significant.

4.0 Changes from Previous Version of Approved SAP

This is the first version of the SAP.

5.0 Study Objectives

This study will investigate the effect of itraconazole treatment on the PK of balovaptan and its major metabolites M2 (RO7045402) and M3 (RO5273004).

5.1 Primary Objective

To investigate the effect of itraconazole treatment on the PK of balovaptan and its major metabolites M2 (as applicable) and M3, at steady state.

5.1.1 Primary PK Endpoints

PK parameters for balovaptan, M2, and M3 after 15 days of balovaptan qd dosing in Period 2, and after 10 days of balovaptan qd dosing in Period 1:

- Maximum observed plasma concentration (C_{max})
- Area under the concentration vs time curve (AUC) over the dosing interval ($AUC_{0-\tau}$)

5.1.2 Additional PK Endpoints

Additional PK endpoints: balovaptan, M2, and M3 time to maximum observed plasma concentration (T_{max}), trough plasma concentration (C_{trough}), and time to steady state

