## 6.6 PHARMACOKINETIC ANALYSES

Subjects will be excluded from the PK analysis population if they significantly violate the inclusion or exclusion criteria, deviate significantly from the protocol, or if data are unavailable or incomplete. Excluded cases will be documented together with the reason for exclusion. All decisions on exclusions from the analysis will be made prior to database closure.

Individual plasma concentrations at each sampling timepoint for balovaptan, M2 (as applicable), M3, itraconazole and hydroxy-itraconazole will be presented by listings and descriptive summary statistics by treatment, including means, geometric means, ranges, standard deviations and coefficients of variation. Individual and mean concentration versus time will be plotted on linear and semi-logarithmic scales.

All PK parameters for balovaptan, M2 (as applicable), and M3 will be presented by individual listings and summary statistics by treatment including means, geometric means, medians, ranges, standard deviations and coefficients of variation.

The following balovaptan PK parameters will be estimated:

- $C_{max}$ : Day 10 of Period 1; Day 15 and Day 20 of Period 2
- $AUC_{0-T}$ : Day 10 of Period 1; Day 15 and Day 20 of Period 2
- $T_{max}$ : Day 10 of Period 1; Day 15 and Day 20 of Period 2
- $C_{trough}$ : Day 10 of Period 1; Day 15 and Day 20 of Period 2)
- time to steady state (for balovaptan)

The primary PK parameters are  $C_{max}$  and  $AUC_{0-T}$  for balovaptan, M2, and M3 on Day 10 of Period 1 and Day 20 of Period 2.

A linear mixed model analysis will be applied to analyze the log-transformed primary PK parameters. The model assumes a fixed effect for treatment and a random effect for subject. Estimates of geometric mean ratios together with the corresponding 90% CIs will be derived for the comparisons of the PK parameters as follows:

- balovaptan plus itraconazole (test) vs balovaptan alone (reference)

For itraconazole and hydroxy-itraconazole,  $C_{max}$ ,  $AUC_{0-24h}$ , and  $T_{max}$  will be estimated on Day 5 and Day 20 to evaluate whether adequate levels were reached.

Additional PK parameters may be derived if deemed necessary.

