7.0 Overview of Planned Analysis

7.1 Changes from Protocol

There are no changes from the protocol.

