16.1.2 Parameters

- PK Parameters for balovaptan, M2, M3, as defined in [Table 1](#).
- PK Parameters for itraconazole and OH-itraconazole, as defined in [Table 1](#)., if feasible.

Table 3 PK Parameter Definitions

Parameter	Description	Balovatan, M2 and M3			itraconazole and OH-itraconazole		SAS Programming Notes
		Analysis Period 1	Analysis Period 3		Analysis Period 2	Analysis Period 3	
		Day 10	Day 10	Day 15	Day 5	Day 15	
C _{max}	Maximum plasma concentration: observed peak analyte concentration obtained directly from the experimental data without interpolation, expressed in concentration units	✓	✓	✓	✓	✓	C _{max} from WNL
T _{max}	Time to maximum plasma concentration: first observed time to reach peak analyte concentration obtained directly from the experimental data without interpolation, expressed in time units.	✓	✓	✓	✓	✓	T _{max} from WNL
AUC _{0-tau}	Area under the concentration-time curve over the dosing interval (time 0 to 24hr).	✓	✓	✓			AUC _{tau} from WNL where tau is equal to 24hr
AUC _{0-24h}	Partial area under the concentration-time curve over the 0 to 24hr				✓	✓	AUC _{0_24} from WNL where partial time =24

Note: AUCs will be calculated using linear up / log down, expressed in units of concentration x time.

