16.2.2 Pharmacokinetic Parameters

PK parameters for balovaptan, M2, and M3 and will be estimated using non-compartmental methods with WinNonlin®.

The plasma PK parameters will be estimated from the concentration-time profiles. In estimating the PK parameters, BQL values will be set to zero for the pre-dose PK sample, as well as for all other samples being BLQ and occurring before T_{max} . For subsequent time points, the result will be set to missing. Actual sampling times, rather than scheduled sampling times, will be used in all computations involving sampling

times. If the actual time or dose time is missing, the scheduled time may be substituted in order to calculate the PK parameter.

Descriptive statistics (number of subjects, arithmetic mean, SD, (arithmetic) CV%, median, min, max, geometric mean and geometric CV%) will be used to summarize the calculated PK parameters by treatment. For T_{max} , only median, min and max will be presented.

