Appendix 4: List of End of Text Outputs

List of End of Text Tables and Figures:		
Output	Title	Population Set
Section 14.1 Disposition and Demographic Data		
Table 14.1.1	Summary of Subject Disposition	Safety
Table 14.1.2.1	Summary of Demographics	Safety
Table 14.1.2.2	Summary of Demographics (if applicable)	PK
Section 14.2 Pharmacokinetic Data		
Table 14.2.1	Individual Values and Descriptive Statistics of Balovaptan Plasma Concentrations by Treatment, Analysis Day and Time-Point	PK
Table 14.2.2	Individual Values and Descriptive Statistics of Balovaptan Plasma Parameters by Treatment and Analysis Day	PK
Table 14.2.3	Individual Values and Descriptive Statistics of Balovaptan Metabolite (M2 and M3) Plasma Concentrations by Treatment, Analysis Day and Time-Point	PK
Table 14.2.4	Individual Values and Descriptive Statistics of Balovaptan Metabolite (M2 and M3) Plasma Parameters by Treatment and Analysis Day	PK
Table 14.2.5	Individual Values and Descriptive Statistics of Itraconazole and OH-Itraconazole Plasma Concentrations by Treatment, Analysis Day and Time-Point	PK
Table 14.2.7	Statistical Analysis of the effect of Itraconazole on Balovaptan	PK
Table 14.2.8	Statistical Analysis of the effect of Itraconazole on Balovaptan Metabolites (M2 and M3)	PK
Figure 14.2.10	Geometric Mean Balovaptan Plasma Concentrations versus Time by Treatment and Analysis Day (Linear and Semi-Logarithmic Scale)	PK
Figure 14.2.11	Geometric Mean Balovaptan Metabolite (M2 and M3) Plasma Concentrations versus Time by Treatment and Analysis Day (Linear and Semi-Logarithmic Scale)	PK
Figure 14.2.12	Geometric Mean Itraconazole and OH-Itraconazole Plasma Concentrations versus Time by Treatment and Analysis Day (Linear and Semi-Logarithmic Scale)	PK
Figure 14.2.13	Combined Individual Balovaptan Plasma Concentrations versus Time by Treatment and Analysis Day (Linear and Semi-Logarithmic Scale)	PK
Figure 14.2.14	Combined Individual Balovaptan Metabolite (M2, M3) Plasma Concentrations versus Time by Treatment and Analysis Day (Linear and Semi-Logarithmic Scale)	PK
Figure 14.2.15	Combined Individual Itraconazole and OH-Itraconazole Plasma	PK

	Concentrations versus Time by Treatment and Analysis Day (Linear and Semi-Logarithmic Scale)	
Figure 14.2.16	Individual Balovaptan Plasma Concentrations versus Time in Days by Treatment (Linear and Semi-Logarithmic Scale)	Safety

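### Does the SAP need a stated rule for time to steady state before the trough data are analysed?

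*SAP*

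**What the plan says.** Protocol Table 1 and SAP section 5.1.2 list the same additional PK endpoints for balovaptan, M2 and M3; in the SAP they end with "trough plasma concentration (C_{trough}), and time to steady state". Protocol section 6.6 includes "time to steady state (for balovaptan" among the parameters to be estimated, so there the scope is the parent alone. It gives no criterion either.

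SAP section 16.1.2 promises "PK Parameters for balovaptan, M2, M3, as defined in" a table of definitions (the cross-reference says Table 1; the definitions are in Table 3). That table covers Cmax, Tmax, AUC0-tau and AUC0-24h, with no row for Ctrough or time to steady state. Section 16.2.2 says the parameters "will be estimated using non-compartmental methods with WinNonlin", and section 16.2.2.1 models only Cmax and AUC0-tau. In Appendix 4 the nearest parameter output, Table 14.2.2, is titled "Individual Values and Descriptive Statistics of Balovaptan Plasma Parameters by Treatment and Analysis Day"; no title mentions time to steady state.

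On deviations, SAP section 3.0 states: "This SAP supersedes the statistical considerations identified in the protocol; where considerations are substantially different, they will be so identified". Section 7.1 states: "There are no changes from the protocol".

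The SAP does plan trough sampling on named days (16.1.1), concentration tables by analysis day and time point (Tables 14.2.1 and 14.2.3), individual concentration-by-day plots (Figures 14.2.16 and 14.2.17) and geometric mean trough plots by day (16.2.1; Figures 14.2.19 and 14.2.20).

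**The concern.** An endpoint named in both documents has no definition and no dedicated output, and the SAP neither drops it nor declares a change. Ctrough can be read straight from a table of predose or 24 h concentrations. Time to steady state cannot, because someone must first decide how close to plateau counts as steady.

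If that decision is taken after the troughs are seen, the result may depend on the choice. Section 3.0 would also treat an analysis that was performed "but not included in this SAP, will be clearly identified in Section 9.8.2 of the CSR", in other words as unplanned. The subject matters to the design: Protocol section 3.3.2.1 justifies 15 days of coadministration by a predicted half-life of about 80 h, and says M2's time to steady state has been assessed only with sparse sampling.

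**Working it through.** **Inputs.** Balovaptan alone: half-life about 46 h after repeat dosing, steady state after approximately 7 days (Protocol 1.2.1.1); around 10 days from population modelling at 10 mg (3.3.2.1). Earlier interaction study: half-life 27 h rising to 80 h, AUC0-inf up 4.6-fold (described as not reliably measured), AUC0-120h up 3.1-fold (1.3). Trough days: SAP 16.1.1.

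**Assumption.** Linear one-compartment accumulation, parent only. The protocol calls the PK dose- and time-dependent and gives no half-life for M2 or M3, so the days below are indicative.

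**1. Reproduce the documents' figures.** Fraction of plateau f(t) = 1 − 2^(−t/T½).
- 46 h, 7 days: 1 − 2^(−168/46) = 0.920
- 46 h, 10 days: 1 − 2^(−240/46) = 0.973
- 80 h, 15 days: 1 − 2^(−360/80) = 0.956

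The 7-day and 10-day figures are therefore compatible with one curve read at about 92% and 97%. The half-life pair is consistent with the reported exposures: 4.6 × (1 − 2^(−120/80)) / (1 − 2^(−120/27)) = 4.6 × 0.646 / 0.954 = 3.12, against the stated 3.1.

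**2. Effect of the criterion.** Days to fraction p = T½ × log2(1/(1−p)) / 24. For example, 80 × 3.322 / 24 = 11.1.

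| T½ | 80% | 90% | 95% | 99% |
|---|---|---|---|---|
| 46 h | 4.5 | 6.4 | 8.3 | 12.7 |
| 80 h | 7.7 | 11.1 | 14.4 | 22.1 |

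From 90% to 95% the time rises by a factor of 1.30, about 2 days at 46 h and 3 days at 80 h. The 99% points lie beyond the last scheduled troughs, at 10 days alone and 15 days with itraconazole.

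**3. What the planned trough output would show.** A predose sample on Day d reflects d − 1 days of dosing. Expected troughs relative to the last one:
- 46 h, Days 3, 5, 8, 9, 10, 11: 0.53, 0.79, 0.95, 0.97, 0.99, 1.00
- 80 h, Days 8, 9, 10, 11, 13, 14, 15, 16: 0.80, 0.85, 0.89, 0.92, 0.96, 0.98, 0.99, 1.00

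The shape of the approach is visible in the tables and Figures 14.2.19 and 14.2.20 without a further model.

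**4. The planned Day 10 and Day 15 comparisons.** Section 16.2.2.1 estimates both ratios to balovaptan alone, with 90% CIs, for all three analytes. On the 80 h curve f(240 h) = 0.875 and f(360 h) = 0.956; 0.956 / 0.875 = 1.09. If exposure is still rising late in coadministration, the two ratios will differ by about that much.

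**5. The primary ratio.** Incomplete accumulation makes the Day 15 AUC ratio 0.956 / 0.973 = 0.982 with 46 h for the reference. With 27 h, f(240 h) = 0.998 and the ratio is 0.956 / 0.998 = 0.958. That is 2% to 4% low, small beside the planned CI factor of 1.30 and the same whichever steady-state rule is used.

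**The case for a change.** The strongest case for a change is that a rule chosen late can shape the message. A stepwise comparison of each trough with the mean of later ones, simulated on the 80 h curve with 12 subjects at the scheduled days, first finds no significant difference at a median of 10, 9, 8, 8 and 7 days for assumed CVs of 10, 15, 20, 25 and 39%. Against 14.4 days for 95% of plateau, that would be a range of about 7 to 14 days on one curve. The remedy would be cheap: a paragraph and one output.

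The dependence on the rule stands, but the wide range does not carry far. Its lower end needs a 39% CV, which the protocol gives for within-subject AUC; neither document states a trough CV. It also needs a significance test, and SAP section 9.4.3 plans no formal testing. Nor does that rule consistently hide a delay from itraconazole: balovaptan alone (46 h) against the combination gives 7 and 10 days at 10% CV, 7 and 8 at 20%, and 4 and 7 at 39%. With no trough between Days 5 and 8, only 4 or 7 days can be returned in that stretch.

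Fixing a particular model would gain little. For a mixed-model exponential fit aimed at 90% of plateau, with a true value of 11.1 days, the simulated 5th to 95th percentiles were 8.3 to 14.8 days at 39% CV and 9.6 to 12.8 at 20%. At the higher CV that spread exceeds the 11.1 to 14.4 day difference between the 90% and 95% rules. The fit also assumes a single exponential for a drug with time-dependent PK, and for metabolites whose half-lives are not given. Statisticians would differ on both the model and the cut-off.

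The declaration of no changes is weak evidence of a fault: the SAP keeps the endpoint, and the protocol had no method from which to depart.

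**Conclusion.** No change to the plan follows. There is a real gap in detail: the endpoint is named, but nothing says how a day is to be read from the troughs, and no output reports one. Analysts can fill this sensibly by describing the approach to plateau from the trough tables and figures, with the Day 10 and Day 15 ratios beside them, and stating the rule in the study report. Section 3.0 already requires unplanned analyses to be identified there.

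The size is about 2 days (46 h) or 3 days (80 h) between a 90% and a 95% rule, assuming one-compartment kinetics and the protocol's half-lives. No data are lost, and the primary ratios do not use the endpoint.

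The remaining points are minor. Analyte scope differs between Protocol section 6.6 (parent only) and Protocol Table 1 and SAP section 5.1.2 (parent, M2 and M3), but the planned trough output covers all three. Ctrough has no row in Table 3, yet its values appear in Tables 14.2.1 and 14.2.3. Section 16.1.1 labels the 24 h sample after the Day 15 dose as a Day 15 trough, although the sentence before it places that sample on Analysis Day 16; this is a clerical slip.
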